#### Response:

## Inclusion criteria:

Children:

- Children in after school programs in XXX Schools (N=294 students at 14 schools)
- Children range in age from 5-13 (grades Kindergarten to 6th grade)
- We will not include any other special population (adults who are unable to consent, prisoners, or economically/educationally disadvantaged individuals)

Adults (Healthy School Leaders):

- after-school program leaders in xxxc Schools
- Recess Aides in schools with after school programs in xxx Schools
- Active, Healthy & Safe team members in schools with after school programs in xxx
- Healthy School Managers in schools with after school programs in xxx Schools
- Physical Education teachers in schools with after school programs in xxx Schools:
- Principals in schools with after school programs in XXX Schools

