#### Response:

We expect to recruit 294 children in grade three to six from 14 schools in xxx School District (about 21 students per school). We expect to recruit about 150 adults (~10 adults per school).

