We will also track student participants' physical activity patterns each semester via accelerometry (total of 4 times) for the 7 intervention schools student participants (n=147), and at the other 7 program schools during their control condition year (n=147). Students will wear ActiGraph GT3X+ accelerometer devices for 24 hours over a period of seven days twice a year. Three members of our research team will visit the after school program to set up the students with devices, and on the following week to collect the devices. Students will initially be shown how to secure the devices using the easy velcro wristband upon arrival at the program in the afternoon by the research team. Participants will wear accelerometers on their wrist to promote greater wear compliance compared to the hip among children. The match-box sized accelerometers are the most commonly used accelerometers in PA research and have been utilized by our research team in studies involving elementary schoolchildren. If a participant loses the accelerometer, they will be asked to immediately inform the front office staff who will inform our research team via email. Each child participant will be assigned a unique unidentifiable number (study ID) which will be linked to a person and used throughout the study.

Students may also be asked to participate in a small group interview for 15 minutes about the changes in their afterschool program at the end of each semester.

The research team will collect attendance, behavioral referral information at the school level without names. As well as demographic information for student participants only (gender, age, race/ethnicity) at all schools from the front office staff at the end of each semester to look for significant relationships between participation in the project and reduced behavior referrals as well as increase attendance. The school district personnel have agreed to the study design and measures. This data will only be collected for participants in this project.

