# https://researchintegrity.asu.edu/human-subjects/special-considerations for more information.

#### Response:

We have incentives for principals, teachers and students.

**Incentives**: Students: \$10 per student per semester x 25 per school x 14 schools

Incentives: Program Leaders: \$50 gift card per leader per semester x 5 per school x 14 schools

Incentives: Healthy School Leaders: \$50 gift card per leader per semester x 5 per school x 14 schools

Note that all participants are participating in both year 1 and 2 either as a comparison or program participant.

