The average enrollment of schools in the study district is 610 students. The average enrollment in all 14 after school programs across schools in the study district is 420 students. Using an estimate of a 70% participation rate among after-school programs and assuming 20% loss-to-follow-up, a sample of 7 intervention and 7 control schools will provide a sample of approximately 294 students (147 intervention and 147 control) at follow-up. Assuming an intra class correlation coefficient of 0.05 with 80% power and an alpha of 0.05, the sample will be sufficient to detect an effect size of .370, similar to other school-based PA interventions reporting small overall effects.

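### The 294 children stated at follow-up is the number before the assumed 20% loss; the plan's own inputs leave about 235

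*SAP*

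**What the plan says.** The SAP (Sample size calculation) gives an enrolment of 420 for the 14 after-school programmes and then proceeds "Using an estimate of a 70% participation rate among after-school programs and assuming 20% loss-to-follow-up". From this it concludes that 7 intervention and 7 control schools "will provide a sample of approximately 294 students (147 intervention and 147 control) at follow-up". With an ICC of 0.05, 80% power and alpha 0.05, it states that "the sample will be sufficient to detect an effect size of .370".

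The protocol uses the same number:

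- IRB section 5 (Number of Participants): "We expect to recruit 294 children in grade three to six from 14 schools", about 21 per school.
- IRB section 4 (Inclusion criteria): "N=294 students at 14 schools", with "Children range in age from 5-13 (grades Kindergarten to 6"th grade).
- IRB section 7 (Study Procedures): accelerometry "for the 7 intervention schools student participants (n=147"), and another 147 in the other seven schools.
- IRB section 8 (Compensation): the student incentive is budgeted "per student per semester x 25 per school x 14 schools", a different count.

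**The concern.** One number cannot be both the sample recruited and the sample left after a fifth of it is lost. The SAP puts 294 at follow-up; the protocol recruits 294. If 294 is the starting number, the attrition allowance has been announced but left out, and the power statement that follows is attached to a sample the trial does not expect to have. Anyone later judging retention against the planned follow-up number would also be using the wrong benchmark.

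A secondary difficulty is which children the 294 are. IRB section 4 describes them as Kindergarten to grade 6, IRB section 5 as grades 3 to 6, and the SAP does not say which grades its 420 covers. If recruitment is limited to grades 3 to 6 while the 420 spans all grades, the 294 would have to be derived again. The documents give no enrolment by grade, so no size can be put on this.

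**Working it through.** **Inputs.** From the SAP: 420 enrolled, read as the total over 14 programmes; participation 0.70; loss 0.20; 7 schools per arm; ICC 0.05; power 80%; alpha 0.05. Sidedness is not stated, and two-sided is assumed here. The SAP's wording calls 420 an average, but only the total reading gives 294, 147 per arm and 21 per school.

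**Reproducing 294.**

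- Without loss: 420 × 0.70 = 294.0; 294/2 = 147; 294/14 = 21 per school. This matches the plan exactly.
- With loss: 294 × 0.80 = 235.2; 235.2/2 = 117.6 per arm; 235.2/14 = 16.8 per school.
- Overstatement: 294/235.2 = 1.25.

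**Could 294 be a true follow-up number?**

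- It would need 294/0.80 = 367.5, so 368 enrolled. That is 367.5/420 = 87.5% participation, against the stated 70%.
- The incentive count is 25 × 14 = 350, which is 350/420 = 83% of enrolment and leaves 350 × 0.80 = 280.
- Neither route gives 294 from the stated inputs.

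**Effect on precision.** This compares the two arms at follow-up, with equal school sizes and no covariate adjustment. With m children per school:

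- Design effect DE = 1 + (m − 1) × 0.05
- SE (in SD units) = √(2 × DE / (7m))
- Detectable effect, normal: (1.960 + 0.842) × SE
- Detectable effect, t with 12 df: (2.179 + 0.873) × SE
- Power at 0.370, normal: Φ(0.370/SE − 1.960); the t version uses the noncentral t with 12 df

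| | 294 (m = 21) | 235 (m = 16.8) |
|---|---|---|
| DE | 2.00 | 1.79 |
| SE | 0.1650 | 0.1745 |
| Detectable effect, normal | 0.462 | 0.489 |
| Detectable effect, t 12 df | 0.503 | 0.532 |
| Power at 0.370, normal | 61% | 56% |
| Power at 0.370, t 12 df | 54% | 50% |

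The ratio of detectable effects is 0.1745/0.1650 = 1.058. It is well below √1.25 = 1.118 because the number of schools does not change, and with an ICC of 0.05 the schools carry much of the variance.

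**The case against.** The arithmetic itself is hard to dispute. The serious objections concern what follows from it.

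**The 0.370 may not have come from 294.** This is fair. The plain formula at ICC 0.05 gives 0.462 for 294 and 0.489 for 235, so neither sample reproduces 0.370. With clustering ignored, 294 gives 0.327 and 235 gives 0.365. The documents do not show which number went into the calculation. They do attribute 0.370 to the sample just described, and that sample is misstated.

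**The consequence is modest.** This also stands. The slip accounts for about 6% in detectable effect and about 5 percentage points of power. The rest of the gap to 0.370 should not be charged to it.

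**The 6% depends on the residual ICC.** Covariate adjustment leaves the ratio unchanged only if it removes the same share of variance between and within schools. Otherwise the residual ICC shifts: the ratio is 1.098 at 0.01, 1.058 at 0.05 and 1.037 at 0.10. The SAP's analysis model also uses baseline and follow-up data, which a follow-up-only formula does not represent. The 6% is therefore tied to the stated ICC of 0.05.

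**Only IRB section 5 speaks of recruiting 294.** Sections 4 and 7 repeat the number without naming a stage. But no section gives a larger enrolled number from which 294 would remain.

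**The grade range is a different matter.** It is an inconsistency of eligibility rather than arithmetic. Other text does not settle it: IRB section 7 refers to a K–6 assessment, while IRB section 12 obtains child assent in grades 3 to 6. The main finding does not depend on it.

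**Conclusion.** The concern holds. On the plan's own inputs, 294 is the number enrolled and about 235 (118 per arm, about 17 per school) is the number expected at follow-up. The SAP's follow-up figure is 25% too large. This rests only on reading 420 as the total over the 14 programmes, which the exact match to 294 supports.

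The cost in precision is small but real: a detectable effect about 6% larger and power for 0.370 lower by about 5 percentage points, under ICC 0.05, two-sided alpha 0.05, equal school sizes and no covariate adjustment. That the stated 0.370 is not reached even with 294 is a separate problem. The contradiction in grade range is genuine but secondary, and no size is claimed for it. This should be corrected, because a stated planning figure is wrong as written.

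**What to change.** In the SAP's sample size section, state 294 enrolled and about 235 at follow-up (about 118 per arm, 17 per school), and base the power statement on 235. Say that 420 is the total over the 14 programmes and which grades it covers.

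Give one grade range in IRB sections 4 and 5 and in the SAP. If it is grades 3 to 6 and the 420 covers Kindergarten to grade 6, derive the sample again from enrolment in grades 3 to 6.

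If the sponsor does intend 294 at follow-up, the SAP must instead state and justify about 368 enrolled (87.5% of 420), or different participation or loss assumptions.

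The recommended correction changes text in both documents and needs no extra recruitment. Its price is a less favourable follow-up number and detectable effect: under the assumptions used here, 0.370 could not be claimed at 80% power.

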A cluster randomized controlled trial of an after-school playground curriculum intervention to improve children's physical, social, and emotional health: Study protocol for the PLAYground project

NCT ID not yet assigned

Date: June 20, 2022

Statistical Analysis Plan

Data analysis

Intervention effects on the primary trial outcomes (at each follow-up time point) will be assessed using general linear mixed effects models to account for the clustering of individual measurements within schools. These will include fixed effects for treatment group (intervention vs control), time (baseline and follow-up), and interaction term (intervention x time); include school as a random effect; and be adjusted for covariates related to the outcome (eg, student sex, age). Analyses related to physical, social, and emotional health will be performed with the child (nested within a school) as the unit of analysis. Analysis related to attendance and behavioral change will be performed with the school as the level of analysis. Separate analyses will be performed at each follow-up time point. Schools will be included in analyses if they meet at least 80% adherence to the protocol.

Secondary implementation outcomes will be assessed using descriptive statistics for Healthy Staff and Student survey data (appropriateness and feasibility) and data from monthly observations (fidelity and sustainability). Frequencies, means, and standard deviations will be calculated to describe the distributions, measures of central tendency, and dispersion of item responses. Data from Healthy Staff and Student interviews will be analyzed using a matrix analysis to summarize and organize data in alignment with Proctor's dimensions (adherence, exposure/dose, quality of delivery, component differentiation, and participant involvement), and content analysis to identify salient themes for each school, by school-level income, and collectively among intervention school groups. We will utilize a deductive approach, but allow for additional themes to emerge.

Sample size calculation

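### The detectable effect of 0.370 does not follow from the SAP's stated inputs, which give 0.46 to 0.50 two-sided (0.41 to 0.44 one-sided)

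*SAP*

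**What the plan says.** The SAP, under Sample size calculation, starts from after-school enrolment: "The average enrollment in all 14 after school programs across schools in the study district is 420 students". It continues: "Using an estimate of a 70% participation rate among after-school programs and assuming 20% loss-to-follow-up", seven schools per arm yield "a sample of approximately 294 students (147 intervention and 147 control) at follow-up". The conclusion drawn is that "the sample will be sufficient to detect an effect size of .370", and the inputs behind it are an ICC of 0.05, power of 80% and a significance level of 0.05. The paragraph likens this to the small effects reported for other school-based physical activity interventions. It gives no formula, sidedness, degrees of freedom, baseline correlation or covariate R-squared.

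The protocol, section 5 (Number of Participants), uses the same number as a recruitment target: "We expect to recruit 294 children in grade three to six from 14 schools", about 21 per school.

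Under Data analysis, the SAP plans a linear mixed model for baseline and follow-up with group, time and their interaction. The model will "include school as a random effect" and adjust for covariates such as sex and age. No child-level random effect is named.

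**The concern.** Every quantity needed for a standard cluster-trial calculation is in the paragraph except sidedness and the reference distribution, so the 0.370 can be checked. It looks too small for a design effect of 2.0 and only 14 schools. In addition, 294 appears both as the number recruited and as the number remaining after a 20% loss.

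This paragraph is the only justification of the sample size in either document. If the figure is unsupported, a reader cannot tell what effect the trial is sized to detect, and a null result could be misread as ruling out effects that the trial had little chance of finding. The comparison with other interventions rests on the same number.

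**Working it through.** **Inputs (SAP, Sample size calculation).** k = 7 schools per arm; 147 children per arm, so m = 147/7 = 21 per school; ICC = 0.05; power 80%; alpha 0.05. The effect size is read as a standardised mean difference. The 420 is read as the total over the 14 programs, since 0.70 × 420 = 294.

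**Attempt to reproduce 0.370.**

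- Design effect: 1 + (21 − 1) × 0.05 = 2.0. Effective size: 147/2.0 = 73.5 per arm.
- Standard error: sqrt(2 × 2.0/147) = 0.1650.
- Detectable effect = multiplier × standard error. Two-sided, the multiplier is 1.960 + 0.842 = 2.802 (normal) or 3.051 (t, 14 − 2 = 12 df).
- Power at 0.370: the standardised effect is 0.370/0.1650 = 2.243. For a two-sided normal test, 2.243 − 1.960 = 0.283, which gives 61%. The t figures use the noncentral t on 12 df.

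| Analysed | Sides | Detectable effect, normal | Detectable effect, t (12 df) | Power at 0.370, normal / t |
|---|---|---|---|---|
| 294 | two | 0.462 | 0.503 | 61% / 54% |
| 294 | one | 0.410 | 0.438 | 73% / 68% |
| 235 | two | 0.489 | 0.532 | 56% / 50% |
| 235 | one | 0.434 | 0.463 | 68% / 64% |

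The 0.370 is not reproduced. The most favourable reading of the stated inputs gives 0.41.

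**Attrition.** 420 × 0.70 = 294, so the participation rate alone yields the number said to remain at follow-up. Applying the loss gives 294 × 0.80 = 235.2, or 16.8 per school and 117.6 per arm. The design effect is 1 + 15.8 × 0.05 = 1.79 and the standard error is sqrt(2 × 1.79/117.6) = 0.1745, which gives the last two rows of the table. Conversely, 294 after a 20% loss needs 294/0.80 = 367.5 enrolled, which is 87.5% of 420 rather than 70%.

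**What would give 0.370 (two-sided).** Each route changes or adds an input:

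- Variance removed by baseline or covariate adjustment: 1 − (0.370/0.462)² = 36% (normal), or 46% (t).
- ICC of about 0.014 (normal) or 0.004 (t) instead of 0.05.
- About 22 schools (normal) or 24 schools (t) of 21 children each.
- Cluster size 610, the average whole-school enrolment quoted in the same paragraph: the design effect is 1 + 609 × 0.05 = 31.45 and there are 7 × 610 = 4,270 per arm, so 3.051 × sqrt(2 × 31.45/4270) = 0.370. This matches, but it contradicts the 294 children. That it was the source is only an inference.

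**The planned group-by-time model.** The documents give no within-child correlation r or covariate R-squared, so the values below are assumptions. The school effect is taken as stable over time.

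- *With a child random effect*, the interaction has variance 4(1 − r)/n, with n per arm. Setting 0.370 equal to the multiplier times the standard error, 80% two-sided power needs r of about 0.36 (normal) to 0.46 (t) with 294 children, or 0.49 to 0.57 with 235.
- *Without a child effect* (only school is named), the model's standard error is sqrt(4 × 0.95/147) = 0.1608, while the true one is sqrt(4(1 − r)/147). At r = 0.4 the true value is 0.1278, and (0.370 − 1.960 × 0.1608)/0.1278 = 0.43, which gives 67%. At r = 0.6 and 0.8 the power is 70% and 77%. One-sided, the three values are 80%, 84% and 92%. If covariates also remove 20% of the residual variance, two-sided power is about 76%, 80% and 88%.

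**The case against.** The strongest objection is that a follow-up-only comparison is not the planned analysis. The SAP's model uses baseline data and covariates, and with a child random effect it would reach 80% two-sided power at 0.370 for a within-child correlation of about 0.36 to 0.46. This stands as a limit on the conclusion: the trial has not been shown to be underpowered. It does not rescue the figure. The sample size paragraph claims no gain from baseline data, and the model section names only a school random effect.

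A second objection is that 0.370 may have been computed with 610 children per school, a number printed in the same paragraph. If so, the cluster size conflicts with the 294 children who are to be analysed, and the figure still needs correcting.

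Third, section 8 of the protocol (Compensation) budgets student incentives for 25 × 14 = 350 children, so more than 294 might be enrolled. That is a budget line, not a recruitment target, and 350 × 0.80 = 280 is still short of 294. It adds a third figure to reconcile and makes the 235-child results conditional on 294 being the number enrolled.

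Finally, the protocol recruits all 14 program schools, so the number of schools is fixed by availability. That limits the practical consequence but not the need for a correct statement of what the trial can detect.

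**Conclusion.** The concern holds: the SAP's figure is wrong as written. On its stated inputs, a follow-up comparison detects 0.46 to 0.50 two-sided, which is 25% to 36% above 0.370, and has 61% to 54% power at 0.370. The one-sided reading gives 0.41 to 0.44, so unstated sidedness does not explain the gap. If 294 children enrol and 20% are lost, the two-sided range is 0.49 to 0.53 and power is 56% to 50%.

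These results rest on equal cluster sizes, a standardised mean difference and the stated ICC. Whether the group-by-time model reaches 80% power at 0.370 cannot be determined. That depends on sidedness, the within-child correlation, the gain from covariates and whether a child random effect is fitted, none of which the SAP settles.

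**What to change.** Recompute with the number of children per school expected in the analysis, after applying the 20% loss. Then take one of two routes:

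- **(a)** Restate the detectable effect for a follow-up comparison (two-sided, about 0.46 to 0.50 with 294 analysed, or 0.49 to 0.53 with 235), or restate the power at 0.370. This is sound on its own.
- **(b)** State a baseline correlation or R-squared, justified independently and not solved backwards from 0.370. Specify a model that uses it, such as one with a child-level random effect, and report the detectable effect that results.

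In either case, give the formula, sidedness, cluster size and degrees of freedom. Reconcile 294 recruited (protocol section 5) with 294 at follow-up (SAP), and with the 350 incentive places in protocol section 8. Base the comparison with other interventions on the corrected figure.

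Route (a) costs SAP wording and a less favourable stated figure. Route (b) costs an explicit, defended assumption and possibly a change to the model. Neither needs extra recruitment.
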